### **7.2.3.2 Events of Clinical Interest**

Selected non-serious and serious adverse events are also known as Events of Clinical Interest (ECI) and must be reported to the Sponsor.

For the time period beginning when the consent form is signed until randomization/treatment allocation, any ECI, or follow up to an ECI, that occurs to any subject must be reported within 24 hours to the Sponsor if it causes the subject to be excluded from the trial, or is the result of a protocol-specified intervention, including but not limited to washout or discontinuation of usual therapy, diet, placebo treatment or a procedure.

For the time period beginning at randomization/treatment allocation through 90 days following cessation of treatment, or 30 days following cessation of treatment if the subject initiates new anticancer therapy, whichever is earlier, any ECI, or follow up to an ECI, whether or not related to the Sponsor's product, must be reported within 24 hours to the Sponsor, either by electronic media or paper. Electronic reporting procedures can be found in the EDC data entry guidelines. Paper reporting procedures can be found in the Investigator Trial File Binder (or equivalent).

Events of clinical interest for this trial include:

1. an overdose of Sponsor's product, as defined in Section 7.2.1 - Definition of an Overdose for This Protocol and Reporting of Overdose to the Sponsor, that is not associated with clinical symptoms or abnormal laboratory results.
2. an elevated AST or ALT lab value that is greater than or equal to 3X the upper limit of normal and an elevated total bilirubin lab value that is greater than or equal to 2X the upper limit of normal and, at the same time, an alkaline phosphatase lab value that is less than 2X the upper limit of normal, as determined by way of protocol-specified laboratory testing or unscheduled laboratory testing.\*

\*Note: These criteria are based upon available regulatory guidance documents. The purpose of the criteria is to specify a threshold of abnormal hepatic tests that may require an additional evaluation for an underlying etiology. The trial site guidance for assessment and follow up of these criteria can be found in the Investigator Trial File Binder (or equivalent).

### **7.2.3.3 Protocol-Specific Exceptions to Serious Adverse Event Reporting**

Efficacy endpoints as outlined in this section will not be reported to the Sponsor as described in Section 7.2.3 - Immediate Reporting of Adverse Events to the Sponsor.

Specifically, the suspected/actual events covered in this exception include any event that is disease progression of the cancer under study.

The Sponsor will monitor unblinded aggregated efficacy endpoint events and other safety data to ensure the safety of the subjects in the trial. Any suspected endpoint which upon review is not progression of the cancer under study will be forwarded to global safety as a SAE within 24 hours of determination that the event is not progression of the cancer under study.

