## 1.0 TRIAL SUMMARY

Abbreviated Title	Phase III Trial of Pembrolizumab (MK-3475), pembrolizumab+FP/XP vs. Placebo+FP/XP in Biomarker Select, Advanced Gastric or GEJ Adenocarcinoma
Trial Phase	III
Clinical Indication	Advanced Gastric or Gastroesophageal Junction (GEJ) Adenocarcinoma
Trial Type	Interventional
Type of control	Active control
Route of administration	Intravenous
Trial Blinding	
Partially Blinded:
 
Treatment Arm 1: Pembrolizumab (monotherapy); the subject, the trial site personnel, the Sponsor and/or designee will not be blinded to this treatment arm since only one type of study medication will be administered on this arm.
 
Treatment Arms 2 and 3: pembrolizumab/placebo is blinded in the combination chemotherapy arms (pembrolizumab+chemotherapy and placebo+chemotherapy, respectively) of this trial to the subject, site personnel and SPONSOR.
 
Pembrolizumab monotherapy (Arm 1) and pembrolizumab/placebo in the combination chemotherapy arms (Arms 2 & 3) will be prepared in a blinded fashion by an assigned unblinded pharmacist or qualified trial site personnel. The investigator or qualified site personnel will administer pembrolizumab/placebo to subjects in Treatment Arms 2 and 3 in a blinded fashion, therefore subjects, site personnel and sponsor personnel are blinded to pembrolizumab/placebo treatment for these 2 arms.

Treatment Groups	
Treatment Arm 1: Pembrolizumab monotherapy 200 mg fixed dose administered every 3 weeks (Q3W)
 
Treatment Arm 2: Pembrolizumab 200 mg fixed dose Q3W + Cisplatin 80 mg/m^2 Q3W + 5-FU* 800 mg/m^2/day continuous IV infusion Days 1-5 (120 hours)
 
Treatment Arm 3: Placebo Q3W + Cisplatin 80 mg/m^2 Q3W + 5-FU* 800 mg/m^2/day continuous IV infusion Days 1-5 (120 hours)
 
*Although use of 5-FU infusion is preferred, capecitabine 1000 mg/m^2 twice a day (BID) D1-14 Q3W may be permitted according to local guidelines. Investigator decision regarding the type of comparator used (5-FU or capecitabine) should be determined prior to randomization. Subjects should continue on the therapy chosen prior to randomization throughout the study. Exceptions may be permitted after consultation with the Sponsor.

Number of trial subjects	Approximately 750 subjects will be enrolled.

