The body surface area (BSA) in m  should be calculated per local guidance. *Although use of 5-FU infusion is preferred, capecitabine 1000 mg/m  bid D1-14 Q3W can be used according to the local guideline. Investigator decision regarding the type of comparator used (5-FU or capecitabine) should be determined prior to randomization in the trial. Subjects should continue on the backbone therapy chosen prior to randomization throughout the study. Exceptions may be permitted after consultation with the Sponsor. Duration of cisplatin treatment may be capped at 6 cycles as per local country guidelines, however treatment with 5-FU/capecitabine may continue per protocol.	

Trial treatment should begin on the day of randomization or as close as possible to the date on which the subject is allocated/assigned.

This study is partially blinded:

**Treatment Arm 1** (pembrolizumab monotherapy); the subject, the trial site personnel, the Sponsor and/or designee will not be blinded to this treatment arm since only one type of study medication will be administered on this arm.

**Treatment Arms 2 and 3** pembrolizumab/placebo is blinded in the combination chemotherapy arms of this trial to the subject, site personnel and SPONSOR personnel.

Pembrolizumab monotherapy (Arm 1) and pembrolizumab/placebo in the combination chemotherapy arms (Arms 2 & 3) will be prepared in a blinded fashion by an assigned unblinded pharmacist or qualified trial site personnel. The investigator or qualified site personnel will administer pembrolizumab/placebo to subjects in Treatment Arms 2 and 3 in a blinded fashion, therefore subject, site personnel and sponsor personnel are blinded to pembrolizumab/placebo treatment for these 2 arms.

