#### **5.2.4 Trial Blinding/Masking**

**This study is partially blinded:**

**Treatment Arm 1:** Pembrolizumab monotherapy, the subject, the trial site personnel, the Sponsor and/or designee will not be blinded to this treatment arm since only one type of study medication will be administered in this arm.

**Treatment Arm 2 and Treatment Arm 3:** Pembrolizumab or placebo treatment in the combination chemotherapy arms (pembrolizumab+chemotherapy and placebo+chemotherapy, respectively) is blinded to the subject, study site personnel and SPONSOR personnel.

Pembrolizumab monotherapy (Arm 1) and pembrolizumab/placebo in the combination chemotherapy arms (Arms 2 & 3) will be prepared in a blinded fashion by an assigned unblinded pharmacist or qualified trial site personnel. The investigator or qualified site personnel will administer pembrolizumab/placebo to subjects in Treatment Arms 2 and 3 in a blinded fashion, therefore subjects, site personnel and sponsor personnel are blinded to pembrolizumab/placebo treatment for these 2 arms.

Even though the trial is only partially blinded (ie treatment arm 1 is open label), the following measures will be taken to help maintain internal blinding: 1) imaging data are

centrally reviewed and the central reviewer is blinded to subject treatment assignment; 2) allocation schedule is blinded in the database preventing aggregate analysis.

See Section 7.1.4.2, Blinding/Unblinding, for a description of the method of unblinding a subject during the trial, should such action be warranted.

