**8.2 Responsibility for Analyses/In-House Blinding**

The statistical analysis of the data obtained from this study will be the responsibility of the Clinical Biostatistics department of the SPONSOR.

Although the trial is partially blinded (pembrolizumab mono therapy arm open label and pembrolizumab in combination with standard of care and standard of care arms are blinded) analyses or summaries generated by randomized treatment assignment and actual treatment received will be limited and documented. In addition, the independent radiologist(s) will perform the central imaging review without knowledge of treatment group assignment.

The SPONSOR will generate the randomized allocation schedule(s) for study treatment assignment for this protocol, and the randomization will be implemented in IVRS.

The DMC will serve as the primary reviewer of the unblinded results of the interim analysis and will make recommendations for discontinuation of the study or modification to an

executive oversight committee of the SPONSOR. Depending on the recommendation of the DMC, the Sponsor may prepare a regulatory submission. If the DMC recommends modifications to the design of the protocol or discontinuation of the study, this executive oversight committee and limited additional sponsor personnel may be unblinded to results at the treatment level in order to act on these recommendations. Additional logistical details, revisions to the above plan and data monitoring guidance will be provided in the DMC Charter.

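### Section 7.2.3.3 has the Sponsor monitor unblinded aggregate efficacy events, which conflicts with the Sponsor blind for Arms 2 and 3 and with the trial-wide bar on aggregate analysis in Section 5.2.4

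*Combined protocol and SAP*

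**What the plan says.** Section 7.2.3.3 removes efficacy endpoint events from immediate reporting. It gives the scope as follows: "the suspected/actual events covered in this exception include any event that is disease progression of the cancer under study". The safeguard offered in return is the sentence at issue: "The Sponsor will monitor unblinded aggregated efficacy endpoint events and other safety data to ensure the safety of the subjects in the trial". The section then has any suspected endpoint that proves not to be progression forwarded to global safety as an SAE.

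The blinding text is elsewhere. Section 1.0 describes blinded administration in Arms 2 and 3 and concludes: "therefore subjects, site personnel and sponsor personnel are blinded to pembrolizumab/placebo treatment for these 2 arms". Section 2.1 says the same: "pembrolizumab/placebo is blinded in the combination chemotherapy arms of this trial to the subject, site personnel and SPONSOR personnel". For Arm 1, Section 1.0 states that "the subject, the trial site personnel, the Sponsor and/or designee will not be blinded to this treatment arm". Section 5.2.4 repeats these positions. It then acknowledges that "the trial is only partially blinded (ie treatment arm 1 is open label), the following measures will be taken to help maintain internal blinding", and the second measure it lists is that the "allocation schedule is blinded in the database preventing aggregate analysis".

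Section 8.2 takes up in-house blinding again. It says that "analyses or summaries generated by randomized treatment assignment and actual treatment received will be limited and documented", makes the DMC the primary reviewer of unblinded interim results, and describes treatment-level unblinding of the executive oversight committee and a few other Sponsor staff when the DMC recommends modifying or stopping the study.

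**The concern.** The three confirmatory looks (IA1, IA2 and the final analysis) are meant to be the occasions on which efficacy is compared by arm, with the DMC between the interim results and the Sponsor. The sentence in Section 7.2.3.3 would permit a continuing unblinded view of progression events inside the Sponsor.

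Those events overlap the primary endpoints. Progression is a component of PFS, which H1 tests for Arm 2 against Arm 3. Section 7.2.3.1 leaves deaths from progression out of expedited SAE reporting, so they fall in the exempted class, and they also count toward OS (H2 to H6).

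The matter has weight because Section 8.0 ties amendments of the primary hypotheses and methods to the period before any unblinding. The document history shows that primary objectives were revised in 2017 and primary OS hypotheses were added in 2018. That history does not suggest misuse. It does mean that the integrity argument relies on a Sponsor blind that the protocol states without contradiction.

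**Working it through.** No plan figure is in dispute, so the check sets the texts side by side.

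1. **Reach of the sentence.** It refers to subjects in the trial, and the exemption it supports covers any progression event. Neither is limited to an arm, and no restricted group within the Sponsor is named.

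2. **Meaning of the wording.** *Aggregated* might be read as pooled over arms. Pooled data that hide treatment are not *unblinded*, however, so that reading leaves the second word without a function. The natural sense is aggregates seen by treatment.

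3. **Against the Sponsor blind.** An unblinded aggregate of Arms 2 and 3 separates pembrolizumab from placebo. Sections 1.0, 2.1 and 5.2.4 withhold that separation from Sponsor personnel. For these two arms the texts cannot both be followed.

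4. **Against the aggregate-analysis measure.** Section 5.2.4 introduces its measures by conceding that Arm 1 is open label, and it does not restrict the database measure to Arms 2 and 3. Individual Arm 1 assignments are known to the Sponsor, but an aggregate of efficacy events by arm is what the measure is said to prevent. The conflict here covers all three arms.

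5. **Search for a reconciling text.**
   - Section 8.2 tolerates limited, documented summaries by treatment. It names no monitoring group and does not mention Section 7.2.3.3, and the treatment-level unblinding it describes follows a DMC recommendation.
   - Sections 7.1.4.2 and 9.3 govern code breaks for individual subjects, which is a separate matter.
   - Section 7.3.3 has the DMC supplement routine monitoring. That allows Sponsor monitoring but does not make it unblinded.
   - The abbreviation list contains an internal standing DMC, but the text gives it no role.

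   None of these resolves the conflict.

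6. **Scope.** With about 750 subjects randomized 1:1:1 (Section 8.9), each arm has 750/3 = 250.
   - Sponsor blind (Arms 2 and 3): 2 × 250 = 500, and 500/750 = 66.7%.
   - Aggregate-analysis measure (all arms): 3 × 250 = 750, or 100%.

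   These are headcounts of the text's reach and do not measure harm.

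7. **Hypotheses touched.** By-arm events in Arms 2 and 3 bear on H1 to H3. Arm 1 events shown apart from the chemotherapy arms bear on H4 to H6, the monotherapy comparisons for OS.

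**The case against.** The strongest reply is that the sentence serves safety. Progression is not an adverse event under Section 7.2 and is exempt from immediate reporting, so some monitoring has to replace that reporting. The sentence schedules no test and changes no alpha or bound. It does not say *by arm* in so many words. The events in question are those met in SAE handling, whereas primary PFS rests on blinded central review. Section 8.2 allows some by-treatment summaries and leaves logistical details, and even revisions to its plan, to a DMC charter that is not among the documents. A restricted Sponsor group could be defined there.

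Much of this stands. It rules out any claim about actual conduct, and it makes Section 8.2 an uneasy fit rather than a flat contradiction. It does not remove the conflict with Sections 1.0, 2.1 and 5.2.4, because a safety purpose can be served by pooled Sponsor monitoring plus by-arm DMC review, and an unseen charter cannot be credited with reconciling the protocol's own text.

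It may also be said that Section 7.1.4.2 repeats the blinding measures and lists only central image review. That omission does not withdraw the measure stated in Section 5.2.4.

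Finally, a reader might infer that Arm 1 is free of the problem because it is open label. The documents open treatment identity in Arm 1. They do not open aggregate efficacy review, and Section 5.2.4 states its measure despite Arm 1's status.

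**Conclusion.** The conflict is real and should be corrected. As worded, Section 7.2.3.3 contradicts the Sponsor blind for Arms 2 and 3 (about 500 subjects) and the bar on aggregate analysis for the whole trial (about 750). Confidence is high on the wording. The impact is conditional on the sentence having been followed literally.

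Three stronger readings are not supported. A reader might infer that the Sponsor saw by-arm results or that type I error was inflated; the documents show no access and give nothing from which an error figure could be derived. A reader might infer that no firewall existed; the most that can be said is that the protocol and SAP describe none for this monitoring and that the charter is unavailable. A reader might infer that the Sponsor should not monitor these events at all; Section 7.3.3 presupposes routine monitoring, and the fault lies in its being unblinded.

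The conclusion assumes that *unblinded* carries its ordinary meaning and that Section 5.2.4 applies to the trial as a whole, as its introduction indicates.

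**What to change.** Replace the sentence in Section 7.2.3.3 with text such as: *For subject safety, the Sponsor will monitor aggregated efficacy endpoint events and other safety data pooled across all treatment arms and without display by treatment assignment. Any review of aggregate endpoint events by treatment arm will be done by the external DMC under its charter, and Sponsor personnel will not have access to it except as stated in Section 8.2.*

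Keep the following sentence on forwarding non-progression events to global safety. Do not add permission to monitor Arm 1 aggregates open label. Set beside the remaining pooled chemotherapy arms, that would authorize a running comparison relevant to H4 to H6.

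Confirm that the DMC charter covers progression events by arm. Section 8.7.1 mentions only AE data for periodic monitoring, and Section 7.2 does not count progression as an AE, so this review could otherwise be left to no one.

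If a separate unblinded Sponsor group was intended, Sections 7.2.3.3 and 8.2 should name it and state its firewall.

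The cost is one sentence becoming two and possibly a matching line in the charter. Event counts, alpha, bounds and power do not change. The Sponsor gives up by-arm aggregate monitoring, which Section 5.2.4 already rules out.

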### **7.2.4 Evaluating Adverse Events**

An investigator who is a qualified physician will evaluate all adverse events according to the NCI Common Terminology for Adverse Events (CTCAE), version 4.0. Any adverse event which changes CTCAE grade over the course of a given episode will have each change of grade recorded on the adverse event case report forms/worksheets.

All adverse events regardless of CTCAE grade must also be evaluated for seriousness.

For studies in which multiple agents are administered as part of a combination regimen, the investigator may attribute each adverse event causality to the combination regimen or to a single agent of the combination. In general, causality attribution should be assigned to the combination regimen (i.e., to all agents in the regimen). However, causality attribution may be assigned to a single agent if in the investigator's opinion, there is sufficient data to support full attribution of the adverse experience to the single agent.

Table 11 Evaluating Adverse Events

An investigator who is a qualified physician, will evaluate all adverse events as to:

V4.0 CTCAE Grading	Grade 1	Mild; asymptomatic or mild symptoms; clinical or diagnostic observations only; intervention not indicated.
	Grade 2	Moderate; minimal, local or noninvasive intervention indicated; limiting age-appropriate instrumental ADL.
	Grade 3	Severe or medically significant but not immediately life-threatening; hospitalization or prolongation of hospitalization indicated; disabling; limiting self-care ADL.
	Grade 4	Life threatening consequences; urgent intervention indicated.
	Grade 5	Death related to AE
Seriousness	
A serious adverse event is any adverse event occurring at any dose or during any use of Sponsor's product that:
 
†Results in death; or
 
†Is life threatening; or places the subject, in the view of the investigator, at immediate risk of death from the event as it occurred (Note: This does not include an adverse event that, had it occurred in a more severe form, might have caused death.); or
 
†Results in a persistent or significant disability/incapacity (substantial disruption of one's ability to conduct normal life functions); or
 
†Results in or prolongs an existing inpatient hospitalization (hospitalization is defined as an inpatient admission, regardless of length of stay, even if the hospitalization is a precautionary measure for continued observation. (Note: Hospitalization for an elective procedure to treat a pre-existing condition that has not worsened is not a serious adverse event. A pre-existing condition is a clinical condition that is diagnosed prior to the use of a Merck product and is documented in the patient's medical history.); or
 
†Is a congenital anomaly/birth defect (in offspring of subject taking the product regardless of time to diagnosis); or
 
Is a cancer (although not serious per ICH definition, is reportable to the Sponsor within 24 hours to meet certain local requirements); or
 
Is associated with an overdose (whether accidental or intentional). Any adverse event associated with an overdose is considered a serious adverse event for collection purposes. An overdose that is not associated with an adverse event is considered a non-serious event of clinical interest and must be reported within 24 hours.
 
Other important medical events that may not result in death, not be life threatening, or not require hospitalization may be considered a serious adverse event when, based upon appropriate medical judgment, the event may jeopardize the subject and may require medical or surgical intervention to prevent one of the outcomes listed previously (designated above by a †).
	
Duration	Record the start and stop dates of the adverse event. If less than 1 day, indicate the appropriate length of time and units	
Action taken	Did the adverse event cause the Sponsor's product to be discontinued?	
Relationship to Sponsor's Product	
Did the Sponsor's product cause the adverse event? The determination of the likelihood that the Sponsor's product caused the adverse event will be provided by an investigator who is a qualified physician. The investigator's signed/dated initials on the source document or worksheet that supports the causality noted on the AE form, ensures that a medically qualified assessment of causality was done. This initialed document must be retained for the required regulatory time frame. The criteria below are intended as reference guidelines to assist the investigator in assessing the likelihood of a relationship between the test drug and the adverse event based upon the available information.
 
The following components are to be used to assess the relationship between the Sponsor's product and the AE; the greater the correlation with the components and their respective elements (in number and/or intensity), the more likely the Sponsor's product caused the adverse event (AE):
	
	Exposure	Is there evidence that the subject was actually exposed to the Sponsor's product such as: reliable history, acceptable compliance assessment (pill count, diary, etc.), expected pharmacologic effect, or measurement of drug/metabolite in bodily specimen?
	Time Course	Did the AE follow in a reasonable temporal sequence from administration of the Sponsor's product? Is the time of onset of the AE compatible with a drug-induced effect (applies to trials with investigational medicinal product)?
	Likely Cause	Is the AE not reasonably explained by another etiology such as underlying disease, other drug(s)/vaccine(s), or other host or environmental factors

Relationship to Sponsor's Product (continued)	The following components are to be used to assess the relationship between the test drug and the AE: (continued)	
	Dechallenge	Was the Sponsor's product discontinued or dose/exposure/frequency reduced? If yes, did the AE resolve or improve? If yes, this is a positive dechallenge. If no, this is a negative dechallenge. (Note: This criterion is not applicable if: (1) the AE resulted in death or permanent disability; (2) the AE resolved/improved despite continuation of the Sponsor's product; or (3) the trial is a single-dose drug trial); or (4) Sponsor's product(s) is/are only used one time.)
	Rechallenge	Was the subject re-exposed to the Sponsor's product in this study? If yes, did the AE recur or worsen? If yes, this is a positive rechallenge. If no, this is a negative rechallenge. (Note: This criterion is not applicable if: (1) the initial AE resulted in death or permanent disability, or (2) the trial is a single-dose drug trial); or (3) Sponsor's product(s) is/are used only one time). NOTE: IF A RECHALLENGE IS PLANNED FOR AN ADVERSE EVENT WHICH WAS SERIOUS AND WHICH MAY HAVE BEEN CAUSED BY THE SPONSOR'S PRODUCT, OR IF REEXPOSURE TO THE SPONSOR'S PRODUCT POSES ADDITIONAL POTENTIAL SIGNIFICANT RISK TO THE SUBJECT, THEN THE RECHALLENGE MUST BE APPROVED IN ADVANCE BY THE SPONSOR CLINICAL DIRECTOR AS PER DOSE MODIFICATION GUIDELINES IN THE PROTOCOL.
	Consistency with Trial Treatment Profile	Is the clinical/pathological presentation of the AE consistent with previous knowledge regarding the Sponsor's product or drug class pharmacology or toxicology?
The assessment of relationship will be reported on the case report forms /worksheets by an investigator who is a qualified physician according to his/her best clinical judgment, including consideration of the above elements.		
Record one of the following	Use the following scale of criteria as guidance (not all criteria must be present to be indicative of a Sponsor's product relationship).	
Yes, there is a reasonable possibility of Sponsor's product relationship.	There is evidence of exposure to the Sponsor's product. The temporal sequence of the AE onset relative to the administration of the Sponsor's product is reasonable. The AE is more likely explained by the Sponsor's product than by another cause.	
No, there is not a reasonable possibility of Sponsor's product relationship	Subject did not receive the Sponsor's product OR temporal sequence of the AE onset relative to administration of the Sponsor's product is not reasonable OR the AE is more likely explained by another cause than the Sponsor's product. (Also entered for a subject with overdose without an associated AE.)	

